7.2 Subjects

Written, informed consent must be obtained from the subjects before any study procedures are initiated. If historical exams and assessments meet specified criteria, they do not need to be repeated.

An independent Sponsor representative (employee of Cochlear[™]) will confirm certain eligibility criteria prior to Randomisation in accordance to inclusion and exclusion criteria. A representative may be either a qualified ENT surgeon, audiologist or qualified subject matter expert. A representative will not participate in any other capacity in the management of the clinical investigation and will be trained on the CIP and Good Clinical Practice (GCP). Following consent of a subject, the site must provide a de-identified audiogram, detailed CT read summary and speech perception results to be reviewed by a representative.

Prior to randomisation of a subject, the representative must have confirmed eligibility, and all screening and baseline assessments must be completed and entered into the EDC in accordance with the Schedule of Events.

Throughout the duration of the clinical investigation, source document records must be maintained to validate subject data.

7.2.1 Inclusion Criteria

Subjects must meet all of the inclusion criteria described below to be eligible for this clinical investigation.

- 1. Postlingual, bilateral, moderate to profound sensorineural hearing loss, defined by a pure-tone average (PTA):
 - a. \geq 40 dB HL at 250 through 1000 Hz and,
 - b. \geq 65 dB HL at 2000 through 8000 Hz.
- 2. Preoperative aided word score is 40% correct or less in the ear to be implanted (60% or less in the contralateral ear).
- 3. 18 years or older at time of consent.
- 4. Willing to be randomised into either a treatment (CI632D) or control (CI632) arm.
- 5. Evidence of pneumococcal vaccination (e.g. Pneumovax) according to local guidelines prior to randomisation.
- 6. Fluent speaker in the local language used to assess clinical performance as judged by the investigator.
- 7. Willing and able to provide written informed consent.

7.2.2 Exclusion Criteria

Subjects who meet any of the exclusion criteria described below will not be eligible for this clinical investigation.

- 1. Deafness due to lesions of the acoustic nerve or central auditory pathway.
- 2. Diagnosed active middle-ear infections or history of middle ear infection within the past six months prior to randomisation. Must not have had surgery, drainage, pain, or need for oral or topical antibiotics within the past six months in the ear to be implanted.
- 3. Previously reported diagnosis of auditory neuropathy.
- 4. Previously reported diagnosis of Large Vestibular Aqueduct Syndrome (LVAS), Meniere's disease, or cochlear hydrops.
- 5. Prior history of surgery in the ear to be implanted (excluding grommets).
- 6. Current use of grommets or evidence of unhealed tympanic membrane perforation.
- 7. Ossification, otosclerosis, malformation or any other cochlear anomaly, such as common cavity, that might prevent complete insertion of the electrode array, as confirmed by imaging.
- 8. Existing cerebrospinal fluid (CSF) shunts or drains, existing perilymph fistula, skull fracture or CSF leaks.
- 9. History of bacterial meningitis.
- 10. Known allergic reaction or contraindication to dexamethasone or corticosteroids.
- 11. Use of ototoxins and/or steroids (does not include topical or inhaled steroids) up to 30 days prior to randomisation.

Note: Systemic ototoxin and/or steroids therapy must be completed at least 7 days prior to Screening/Baseline audiometric and speech testing

- 12. Evidence of severe or greater sensorineural hearing loss prior to five years of age, as reported by the subject.
- 13. Severe to profound sensorineural hearing loss for more than 20 years, as reported by the subject.
- 14. Existing contralateral cochlear implant.
- 15. Medical plan to implant a contralateral cochlear implant during the clinical investigation.
- 16. History of recurrent otitis media or chronic otitis media in the ear to be implanted within the past six months prior to randomisation.
- 17. Medical or psychological conditions that contraindicate general anaesthesia, surgery or participation in the clinical investigation.
- 18. Pregnant or breastfeeding women. Women who plan to become pregnant during the course of the investigation.
- 19. Unrealistic expectations on the part of the subject, regarding the possible benefits, risks, and limitations that are inherent to the surgical procedure(s) and prosthetic devices as determined by the Investigator.
- 20. Additional disabilities that may affect the subject's participation or safety during the clinical investigation.
- 21. Unable or unwilling to comply with all the requirements of the clinical investigation as determined by the Investigator.
- 22. Investigator site personnel directly affiliated with this study and/or their immediate families; immediate family is defined as spouse, parent, child, or sibling.
- 23. Cochlear™ employees or employees of Contract Research Organisations or contractors engaged by Cochlear for the purposes of this investigation.
- 24. Currently participating, or participated within the last 30 days, in another interventional clinical investigation/trial involving an investigational drug or device.

7.2.3 Number of Subjects Required

Up to 120 subjects will be randomised into the clinical investigation. Randomisation is 1:1 to the treatment or control arm. See Section 9.4 for the sample size calculations.

The clinical investigation will be completed under a group sequential design where analysis of the primary endpoints occurs following the 6-month endpoint for the first 50 randomised subjects. If stopping criteria (see Section 9.10) are not met at this first analysis of both primary endpoints, then enrolment will continue, and analysis will be completed again for the first 80 randomised subjects at 6 months post-cochlear implant. If stopping criteria are not met again, then enrolment will continue, and analysis will be completed again for the first post-cochlear implant. If stopping criteria are not met again, then enrolment will continue, and analysis will be completed again for the first 100 randomised subjects at 6-months post-cochlear implant. If stopping criteria is not met again enrolment will continue for a total of 120 subjects. Enrolment does not need to stop for group analysis and the Sponsor may choose to randomise 120 subjects to capture more data for other endpoint analyses.

7.2.4 Vulnerable Populations

The clinical investigation aims to treat individuals with post-lingual, bilateral, moderate to profound hearing loss. There is a risk that subjects will have difficulty completing the informed consent process due to limited hearing and potential cognitive impairments, which may be associated with hearing impairment. Recruitment must include processes to ensure the investigator discusses the informed consent with all subjects and all questions are answered to the subject's satisfaction. Additional measures taken to review the study with potential subjects must be documented in the informed consent process. The Ethics Committee (EC) may have additional requirements which must be followed.

IMD and comparator devices may be provided at no cost to the subject or hospital. This financial model may provide added benefit to potential subjects and clinical investigation sites. Subjects may be compensated for their time in the clinical investigation in alignment with fair market value. The informed consent process must include ensuring subjects are not choosing to participate for the financial benefits, and site personnel must not use the financial model to coerce subjects to participate in the clinical investigation.

Women that are pregnant, breastfeeding or women who plan to become pregnant during the clinical investigation are excluded from participation. Women of childbearing potential will be required to take a pregnancy test prior to randomisation and agree to use appropriate (as deemed by the Investigator) methods to avoid becoming pregnant during their participation in the clinical investigation.

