3 SCHEDULE OF EVENTS

Visit Type	Screening /Baseline	Randomisatio n	Surgery	Visit 1	Visit 2ª	Visit 3	Visit 4	Visit 5	Visit 6	Visit 7	EOS
Timing of Investigation		≤90 Days before Surgery	Day 0	10 Days after Surgery	15 Days after Surgery (Activation)	30 Days after Activation	3 Months after Surgery	6 Months after Surgery	9 Months after Surgery	12 Months after Surgery	
Visit window (±)				1-10 days	± 7 days	± 5 days	90 days, ± 14 days	180 days, ± 14 days	270 days, ± 30 days	365 days, +30 days	
Procedures											
Written informed consent ^b	x										
Demographics	X										
Eligibility	X										
Hearing history	X										
Device history	X										
Medical history	X										
Audiogram	Xc					X	x	х	х	х	
Speech Perception testing	Xc						x	x		x	

^a Visits 1 and 2 may be conducted in combination (i.e., Visit 1+2), occurring within a single session on the same day, as long as the visit occurs within the compliance window indicated above. Specifically, Visit 1+2 can occur 8-10 days post surgery. Assessments that are required for Visits 1+2 only need to be completed once and should be recorded on Visit 2. If sites cannot schedule Visit 1+2 within 8-10 days post surgery, the two visits should remain separated (i.e., Visit 1 & Visit 2) and occur within their respective time window as indicated above.

^b Written informed consent must be obtained prior to completing study specific assessments, assigning a subject identification code and entering data into EDC.

^c Baseline audiogram and speech perception testing must be completed within 90 days prior to Randomisation.

Clinical Investigation Plan | Approval Date (GMT+

Visit Type	Screening /Baseline	Randomisatio n	Surgery	Visit 1	Visit 2ª	Visit 3	Visit 4	Visit 5	Visit 6	Visit 7	EOS
Timing of Investigation		≤90 Days before Surgery	Day 0	10 Days after Surgery	15 Days after Surgery (Activation)	30 Days after Activation	3 Months after Surgery	6 Months after Surgery	9 Months after Surgery	12 Months after Surgery	
Visit window (±)				1-10 days	±7 days	± 5 days	90 days, ± 14 days	180 days, ± 14 days	270 days, ± 30 days	365 days, +30 days	
Imaging	High Resolution CT ^d		HRCT, Intra- op X-ray or fluorosopy ^e		High Reso	olution CT ^f					
Hearing-Impaired Montreal Cognitive Assessment Impaired (HI- MoCA)	Xg										
Health Utilities Index III (HUI3)	Xg					x	х	x		x	
Dizziness/Tinnitus Questionnaire (DTQ)	Xg					x	x	x	х	х	
Dizziness Handicap Inventory (DHI)	Xg					x	x	x	x	x	

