7.2.5 Recruitment and Study Duration

The following subject status definitions apply:

- Enrolled: A subject that has a signed the Informed Consent form for the study.
- Screen Fail: An Enrolled subject that has been determined to not meet one or more eligibility criteria.
- Participated: Consented subjects who have met all eligibility criteria, have qualified for surgery, and have been randomised.
- Implanted: A participating subject who has received the IMD/comparator in accordance to the randomisation assignment
- Treatment Failure: A participating subject who has not been successfully implanted or does not receive the IMD or comparator treatment in accordance with the randomisation assignment
- Discontinued: An Enrolled subject who withdrew consent, was discontinued by the Investigator or Sponsor before the expected End of Study visit or lost to follow-up. Discontinued subjects may still have safety follow up data collection until their scheduled End of Study visit, for reasons described in section 7.2.6.
- Completed: Enrolled subjects who complete the required treatment and visit schedule.

The recruitment period for the clinical investigation is estimated to be 28 months from the time of first subject consent to recruitment of the last subject. If the recruitment numbers increase following the interim analysis, the recruitment period is expected to extend approximately one month for every eight enrolments.

The expected duration of each subject's participation in the clinical investigation, is 14 months. From the time of implant through to the End-of-Study visit is 12 months after implantation.

Therefore, the anticipated total duration of the clinical investigation is 42 months. Clinical Investigation completion is at the last subject's last visit. In the event of ongoing SAEs/SADEs at the time of a subject's last visit, the subject's clinical investigation completion will be extended for a further 30 days, or until resolution or stabilisation of the event, whichever comes first.

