7.3.1 Screening/eligibility

Screening and Baseline may be completed in parallel. If historical exams are available, they must be within the timeframes indicated below. The following must be completed prior to Randomisation:

- Written informed consent: must be completed before any study specific procedures are completed.
- Demographics: document age and sex.
- Eligibility: confirm subject meets all inclusion criteria and no exclusion criteria (see section 7.2.1 and 7.2.2). Source documentation must be available before confirming eligibility.
- Hearing History: document history of hearing loss (may be subject reported)
- Device history: document history with hearing aids and cochlear implant (contralateral ear) (may be subject reported)
- Medical History: document medical history.

- Audiogram: must be completed less than 90 days prior to randomisation and document bilateral, moderate to profound hearing loss. (see section 7.3.2.2)
- Speech Perception testing: must be completed less than 90 days prior to randomisation. Subject's own or loaner hearing aid must be optimally fitted using National Acoustics Laboratories' hearing aid fitting formula to confirm eligibility for clinical investigation. (see section 7.3.2.3)
- High Resolution CT imaging: must be completed within 2 years prior to randomisation and show entire cochlea per the imaging protocol. (see section 7.3.1.6)
- Health Survey (HS): must be completed within 90 days prior to randomisation. (see section 7.3.2.1)
- Hearing-Impaired Montreal Cognitive Assessment (HI-MoCA): must be completed within 90 days prior to randomisation. (see section 7.3.2.1)
- Health Utilisation Index III (HUI3): must be completed within 90 days prior to randomisation. (see section 7.3.2.1)
- Dizziness/Tinnitus Questionnaire (DTQ): must be completed within 90 days prior to randomisation. (see section 7.3.2.1)
- Dizziness Handicap Inventory (DHI): must be completed within 90 days prior to randomisation as required by DTQ. (see section 7.3.2.1)
- Tinnitus Handicap Inventory (THI): must be completed within 90 days prior to randomisation as required by DTQ. (see section 7.3.2.1)

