7.3.2. Performance/Effectiveness

7.3.2.1. Description of Questionnaires

The following subject facing questionnaires will be completed during the clinical investigation at specified Visits:

- Hearing-Impaired Montreal Cognitive Assessment (HI-MoCA): clinician guided questionnaire that assists in the detection of cognitive impairment. The questionnaire was developed by V. Lin and Sunnybrook Health Sciences Centre (Toronto, Canada).
- Health Survey (HS): clinician guided questionnaire to review for potential inflammatory conditions. The questionnaire was developed by the Sponsor.

The Health Survey (HS) is a clinician guided questionnaire that was developed by the Sponsor to collect health-related data that may be linked to inflammatory conditions that could affect impedance measurements. These include:

- Body temperature
- Blood pressure
- Menstrual cycle phase (if appropriate)
- Relevant medical history, including arthritis, allergies, frequent headaches, other chronic inflammatory conditions [information is captured in the Medical History form]

- Use of antibiotic or anti-inflammatory medication [information captured in the Concomitant Medications Form]
- Other applicable informationHealth Utilities Index III (HUI3): a self-administered questionnaire that includes a rating scale used to measure general health status and health-related quality of life (HRQoL). The questionnaire was developed by Health Utilities Inc.
- Dizziness/Tinnitus Questionnaire (DTQ): clinician guided questionnaire to review dizziness and tinnitus characteristics. The questionnaire was developed by the Sponsor.
- Dizziness Handicap Inventory (DHI): self-administered questionnaire that includes a scale to identify difficulties that you may be experiencing because of dizziness. The questionnaire was developed by Dr. G.P. Jacobson and Dr. C.W. Newman.
- Tinnitus Handicap Inventory (THI): self-administered questionnaire that identifies difficulties that you may be experiencing because of tinnitus. The questionnaire was developed by Dr. C.W. Newman, Dr. G.P. Jacobson, and Dr. J.B. Spitzer.
- Blinding Questionnaire (BQ): self-administered questionnaire to assess subject's understanding of randomisation assignment. The questionnaire was developed by the Sponsor.

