7.3.2.7.2. Randomisation

Randomisation may only be completed once all activities under Screening and Baseline are completed, subject screening/baseline data is entered into the EDC, and eligibility has been confirmed by an independent Sponsor representative.

The ear to be implanted will need to be determined prior to randomization and must be compliant with the inclusion and exclusion criteria. The decision will be made between the investigator, audiologist and subject, and the justification for ear selection must be documented.

7.3.2.7.3. Surgery (day 0)

Data collection from time of Surgery through discharge from hospital includes:

• High Resolution CT: Post insertion to assess electrode placement. Cone beam CT and flat panel CT are examples.

OR

- X-Ray or fluoroscopy (C-arm): required intraoperatively to assess placement of electrode using Modified Stenver's View. X-ray or fluorscopy will be repeated if electrode is repositioned/replaced.
 - If final placement of cochlear implant is not positioned correctly (tip foldover or translocation), the subject will remain in the clinical investigation and complete all assessments. Outcome will be documented in the CRF.
- Electrode Electrical Testing: must be completed intraoperatively after final placement of electrode. If electrode position is altered or second device is used, testing must be repeated. Complete tests in the following order:
 - 1. Impedances (MP1+2 and Four point).
 - 2. AutoNRT[®] (standard 9 electrodes).
- Surgical Questionnaire: surgeon's review of surgical implant.
- Discharge Summary: subject's stay in hospital.

The following requirements are to be followed for the Surgery:

- At the surgeon's discretion, dexamethasone may be utilised in anaesthesia, IV and take-home pack, which will be documented in the CRF.
- Dexamethasone may not be used to treat (e.g. topically) the cochlear implant electrode.
- Dexamethasone may not be used within or near the ear/cochlea.
- Cochlear implant electrode may not be dipped in saline, hyaluronic acid (healon), or other treatment prior to insertion.
- The implant procedure must follow Instructions for Use (IFU). A back up CI632D or CI632 may be required if preparation/insertion is not possible according to IFU.
- Following impedance and/or NRT testing, if the electrode is re-inserted or replaced with a new device, the testing must be repeated

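### The only required pregnancy test precedes randomisation, surgery may follow up to 90 days later, and pregnancy status is not re-checked before implantation

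*Protocol*

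**What the plan says.** - **Exclusion 18 (7.2.2):** "Pregnant or breastfeeding women. Women who plan to become pregnant during the course of the investigation".
- **The test (7.2.4):** "Women of childbearing potential will be required to take a pregnancy test prior to randomisation". The same sentence has these women "agree to use appropriate (as deemed by the Investigator) methods to avoid becoming pregnant during their participation". No look-back window is given for the test.
- **Confirming eligibility (7.3.1):** all criteria are confirmed before randomisation, and "Source documentation must be available before confirming eligibility". The section gives time windows for the audiogram, speech tests, CT and questionnaires, but does not list the pregnancy test.
- **Time to surgery (Schedule of Events):** randomisation is placed "≤90 Days before Surgery". The Eligibility row is marked only at Screening/Baseline, and there is no pregnancy-test row. A footnote adds that the subject need not come to the clinic for randomisation.
- **Surgery (7.3.2.7.3):** the list that opens "The following requirements are to be followed for the Surgery" covers steroid use, electrode handling, adherence to the instructions for use and repeat electrical testing. It contains no check of pregnancy status.
- **Duration (7.2.5):** "The expected duration of each subject's participation in the clinical investigation, is 14 months", of which 12 months follow implantation.

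**The concern.** The protocol fixes when the test is done, but ties it to the wrong event. Nothing is administered at randomisation. The exposures relevant to exclusion 18 begin at surgery: general anaesthesia, intra-operative X-ray or fluoroscopy (or a post-insertion CT), any systemic dexamethasone the surgeon chooses to give and, in the CI632D arm, the eluting electrode. All but the last apply to both arms.

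A site that follows the protocol exactly could implant a woman who conceived after her test, and no required step would detect it. What is at stake is subject safety and whether the sponsor's own exclusion holds when it matters. The statistical analysis is not at stake.

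**Working it through.** **1. How old can the test be at surgery?**

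Age at surgery = (test to randomisation) + (randomisation to surgery).

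- The second term is 0 to 90 days (Schedule of Events).
- The first term is 0 days or more, because 7.2.4 sets no window.
- A test on the day of randomisation: 0 + 90 = 90 days at most. This is the figure used below.
- A test done alongside baseline audiometry, which may fall up to 90 days before randomisation: 90 + 90 = 180 days. The text does not rule this out.

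**2. How long is the planned gap?**

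Section 7.2.5 implies 14 − 12 = 2 months, about 60 days, from entry to implant. This includes consent and screening, so the planned interval from randomisation to surgery is shorter.

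**3. Is status re-checked in between?**

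The Schedule of Events, 7.2.4, 7.3.1, 7.3.2.7.2 and 7.3.2.7.3 contain no repeat test and no second confirmation of eligibility. The Health Survey is scheduled at baseline and from Visit 1, but not at surgery. It asks about menstrual phase because of possible effects on impedance and is not a pregnancy screen, so nothing here rests on it.

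**4. Expected number of pregnancies arising in the gap**

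The protocol gives neither the number of women of childbearing potential nor a pregnancy rate. Assumptions:

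- women: 5% to 20% of 120 subjects, so 0.05 × 120 = 6 to 0.20 × 120 = 24;
- rate: 1 to 10 per 100 woman-years despite contraception, so 0.01 to 0.10 per year;
- every woman waits the whole interval.

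Expected number = women × annual rate × days / 365.

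| Untested gap | Lowest case | Highest case |
|---|---|---|
| 90 days | 6 × 0.01 × 90/365 = 0.015 | 24 × 0.10 × 90/365 = 0.59 |
| 60 days | 6 × 0.01 × 60/365 = 0.010 | 24 × 0.10 × 60/365 = 0.39 |
| 7 days (with a repeat test) | 6 × 0.01 × 7/365 = 0.001 | 24 × 0.10 × 7/365 = 0.046 |

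**5. Effect of a repeat test on the unchecked interval**

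- From 90 days: 1 − 7/90 = 92% shorter.
- From 60 days: 1 − 7/60 = 88% shorter.

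These percentages describe days. They carry over to expected pregnancies only because step 4 assumes a constant rate.

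**The case against.** The strongest reply is that this is a choice of safeguard and not a fault. The protocol confirms all eligibility before randomisation, and other time-sensitive exclusions, such as recent middle-ear infection and steroid use, are also dated to randomisation and not repeated at surgery. The main control is continuous: contraception is agreed for the whole of participation, and women planning pregnancy are excluded. The investigator may withdraw a subject in her interest, ethics committees may add requirements, and the instructions for use, the Investigator's Brochure and the consent form are not at hand. Section 8.3 says the surgical risks are those a subject would face outside the trial and calls the drug-related risk minimal. Section 8.5 puts the dexamethasone load about 15- to 110-fold below local doses in cited studies. The size estimate also rests on assumed inputs and spans about 40-fold (0.59 / 0.015 = 39).

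Much of this stands. The added risk specific to the trial is small, the rates are assumptions, and the top of the range needs the largest group, the highest rate and the longest wait together. None of it verifies pregnancy status at surgery, however. A contraception agreement is not a test. Routine hospital testing may happen, but the protocol neither requires nor records it across 5 to 25 sites in three countries. The small eluted dose does not bear on anaesthesia or imaging. The sponsor judged the exclusion necessary, so it should hold when exposure begins.

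**Conclusion.** The concern holds, as a low-probability safety gap that is worth closing because closing it is cheap. The protocol allows at least 90 days between its only pregnancy test and implantation, with no re-check. On the assumptions above, the expected number of pregnancies arising in that gap is 0.01 to 0.59 over 90 days, or 0.01 to 0.39 over the planned 60 days or so, across the whole trial. The 90 days comes directly from the Schedule of Events; the counts depend on the assumed number of women and the assumed rate.

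This is an omission and not a contradiction: the requirement in 7.2.4 remains binding although 7.3.1 and the Schedule do not list it.

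**What to change.** Keep the test before randomisation and list it in 7.3.1 and the Schedule of Events as a Screening/Baseline item. Add to 7.3.2.7.3, with a matching mark in the Surgery column:

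> For women of childbearing potential, repeat urine pregnancy test within 7 days before surgery, with a negative result recorded before anaesthesia. If positive, do not implant; record the subject as Treatment Failure (7.2.5).

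The 7 days is an assumption; any point from 14 days before surgery to the day itself would serve.

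**Cost:** one urine test per woman of childbearing potential at the pre-operative or admission contact, one Schedule row, and one line each in 7.3.1 and 7.3.2.7.3. No extra visit is needed. An eCRF field may have to be added; whether one exists cannot be seen. A positive result would produce a randomised subject who cannot be replaced (7.1, 7.2.6), stays in the intent-to-treat population (9.5) and has her missing outcomes handled by multiple imputation (9.6.1). On the figures above this should be rare.
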